5.3 Lifestyle restrictions

The following restrictions apply while the patient is receiving IP and for the specified times before and after:

- 1 Female patients of childbearing potential
 - (a) Female patients of childbearing potential who are not abstinent and intend to be sexually active with a non-sterilized male partner must use at least 1 **highly** effective method of contraception (Table 4) from the time of screening throughout the total duration of the drug treatment and the drug washout period (90 days after the last dose of durvalumab [MEDI4736] monotherapy). Non-sterilized male partners of a female patient of childbearing potential must use a male condom plus spermicide throughout this period. Cessation of birth control after this point should be discussed with a responsible physician. Periodic abstinence, the rhythm method, and the withdrawal method are not acceptable methods of contraception. Female patients should refrain from breastfeeding throughout this period.
- 2 Male patients with a female partner of childbearing potential
 - (a) Non-sterilized male patients who are not abstinent and intend to be sexually active with a female partner of childbearing potential must use a male condom plus spermicide from the time of screening throughout the total duration of the drug treatment and the drug washout period (90 days after the last dose of durvalumab [MEDI4736] monotherapy). Periodic abstinence, the rhythm method, and the withdrawal method are not acceptable methods of contraception. Male patients should refrain from sperm donation throughout this period.

- (b) Female partners (of childbearing potential) of male patients must also use a highly effective method of contraception throughout this period (Table 4).

Please note, females of childbearing potential are defined as those who are not surgically sterile (ie, bilateral salpingectomy, bilateral oophorectomy, or complete hysterectomy) or post-menopausal.

Women will be considered post-menopausal if they have been amenorrheic for 12 months without an alternative medical cause. The following age-specific requirements apply:

- Women <50 years of age would be considered post-menopausal if they have been amenorrheic for 12 months or more following cessation of exogenous hormonal treatments and if they have luteinizing hormone and follicle-stimulating hormone levels in the post-menopausal range for the institution.
- Women \geq 50 years of age would be considered post-menopausal if they have been amenorrheic for 12 months or more following cessation of all exogenous hormonal treatments, had radiation-induced menopause with last menses >1 year ago, had chemotherapy-induced menopause with last menses >1 year ago.
- Women who are surgically sterile (ie, bilateral salpingectomy, bilateral oophorectomy, or complete hysterectomy) are eligible.

Highly effective methods of contraception, defined as one that results in a low failure rate (ie, less than 1% per year) when used consistently and correctly are described in Table 4. Note that some contraception methods are not considered highly effective (eg, male or female condom with or without spermicide; female cap, diaphragm, or sponge with or without spermicide; non-copper containing intrauterine device; progestogen-only oral hormonal contraceptive pills where inhibition of ovulation is not the primary MOA [excluding Cerazette/desogestrel which is considered highly effective]; and triphasic combined oral contraceptive pills).

Table 4 Highly effective methods of contraception (<1% failure rate)

| Barrier/intrauterine methods | Hormonal methods |
|---|--|
| 
 • Copper T intrauterine device • Levonorgestrel-releasing intrauterine system (eg, Mirena[®])^a | 
 • Implants: Etonogestrel-releasing implants (eg, Implanon[®] or Norplant[®]) • Intravaginal devices: Ethinylestradiol/etonogestrel-releasing intravaginal devices (eg, NuvaRing[®]) • Injection: Medroxyprogesterone injection (eg, Depo-Provera[®]) • Combined pill: Normal and low dose combined oral contraceptive pill • Patch: Norelgestromin/ethinylestradiol-releasing transdermal system (eg, Ortho Evra[®]) • Minipill: Progesterone-based oral contraceptive pill using desogestrel (Cerazette[®] is currently the only highly effective progesterone-based pill) |

^a This is also considered a hormonal method.

- 3 All patients: Patients should not donate blood or blood components while participating in this study and through 90 days after receipt of the final dose of IP or until alternate anticancer therapy is started.
- 4 Restrictions relating to concomitant medications are described in Section 6.4.

5.4 Patient enrolment

All patients will be centrally assigned to study drug using an Interactive Voice Response System (IVRS)/Interactive Web Response System (IWRS). Before the study is initiated, the telephone number and call-in directions for the IVRS and/or the log-in information and directions for the IWRS will be provided to each site.

At screening/baseline (Days -28 to -1), the Investigators or suitably trained delegate will:

- 1 Obtain signed informed consent from the potential patient before any study specific procedures are performed that are not part of routine medical care.
- 2 Obtain a unique 7-digit enrolment number (E-code), through the IVRS/IWRS. This number is the patient's unique identifier and will be maintained throughout the study.
- 3 Determine patient eligibility (see Section 5.1 and 5.2).
- 4 Obtain signed informed consent for genetic research study (optional and where applicable).

Patients will begin treatment on Day 1. If a patient does not meet eligibility criteria or withdraws from participation in the study after enrolment, then his/her E- number cannot be

reused. Investigator(s) should keep a record/screening log of patients who entered pre-study screening.

5.5 Procedures for handling incorrectly enrolled patients

Patients who fail to meet the eligibility criteria should not, under any circumstances, be enrolled or receive the study drug. There can be no exceptions to this rule. Patients who are enrolled, but subsequently found not to meet all the eligibility criteria, must not be initiated on treatment, and must be withdrawn from the study.

Where a patient does not meet all the eligibility criteria but is incorrectly started on study drug, the Investigator should inform the AstraZeneca Study Physician immediately, and a discussion should occur between the AstraZeneca Study Physician and the Investigator regarding whether to continue or discontinue the patient from the study drug. The AstraZeneca Study Physician must ensure all decisions are appropriately documented and that the potential benefit/risk-profile remains positive for the patient.

5.6 Screen failures

Screen failures are patients who do not fulfil the eligibility criteria for the study, and therefore must not be dosed. These patients should have the reason for study withdrawal recorded as “screen failure”. This reason for study withdrawal is only valid for screen failures (ie, not for patients who are assigned IP treatment). Patients may be re-screened a single time, but they may not be re-assigned IP treatment. If a patient who has failed screening is re-screened, a new E-code must be assigned. Patients will reconfirm their consent to participate in the study by re-signing and dating their original consent form(s), next to their initial signature and date.

A minimal set of screen failure information is required to ensure transparent reporting of screen failure patients to meet the Consolidated Standards of Reporting Trials (CONSORT) publishing requirements and to respond to queries from regulatory authorities. Minimal information includes demography, screen failure details, eligibility criteria, and any SAE.

6 STUDY TREATMENTS

Study treatment is defined as any IPs (including marketed product comparator and placebo) intended to be administered to a study participant according to the study protocol. Study treatment in this study refers to durvalumab (MEDI4736).

6.1 Treatments administered

6.1.1 Investigational product

AstraZeneca will supply durvalumab (MEDI4736) (described in [Table 5](#)).

Table 5 Study treatment

| | |
|----------------------------------|--|
| Study treatment name | Durvalumab (MEDI4736) |
| Dosage formulation | 500-mg vial solution for infusion after dilution, 50 mg/mL |
| Route of administration | IV |
| Dosing instructions ^a | 1500 mg IV q4w ^b |
| Packaging and labelling | Provided in 500-mg vials, labelled in accordance with GMP Annex 13 and per country regulatory requirement ^c |
| Provider | AstraZeneca |

^a Refer to Section 6.1.3 for details on duration of treatment and criteria for treatment through progression.

^b If a patient's weight decreases to ≤ 30 kg, the patient should receive weight-based dosing equivalent to 20 mg/kg of durvalumab (MEDI4736) q4w until the weight improves to >30 kg, at which point the patient should start receiving the fixed dosing of durvalumab (MEDI4736) 1500 mg q4w.

^c Label text will show the product name as "MEDI4736" or "durvalumab (MEDI4736)" depending upon the agreed product name used in the approved study master label document. All naming conventions are correct during this transitional period.

Note: Cycles of durvalumab (MEDI4736) administration are 28 days.

GMP: Good Manufacturing Practice; IP: Investigational product; IV: Intravenous; q4w: Every 4 weeks.

Durvalumab (MEDI4736) will be supplied by AstraZeneca as a 500-mg vial solution for infusion after dilution. The solution contains 50 mg/mL durvalumab (MEDI4736), CCI

CCI

The label claim fill volume

is 10.0 mL.

Durvalumab is a sterile, clear to opalescent, colorless to slightly yellow solution, free from visible particles.

IP vials are stored at 2°C to 8°C (36°F to 46°F) and must not be frozen. Investigational product should be kept in original packaging until use to prevent prolonged light exposure.

Preparation of durvalumab (MEDI4736) doses for administration with an IV bag

The dose of durvalumab (MEDI4736) for administration must be prepared by the pharmacist using aseptic technique. Total time from needle puncture of the durvalumab (MEDI4736) vial to the start of administration should not exceed:

- 24 hours at 2°C to 8°C (36°F to 46°F)
- 4 hours at room temperature

If the final product is stored at both refrigerated and ambient temperatures, the total time should not exceed 24 hours.

A dose of 1500 mg (for patients >30 kg in weight) will be administered using an IV bag containing 0.9% (w/v) saline or 5% (w/v) dextrose, with a final durvalumab (MEDI4736)

concentration ranging from 1 to 20 mg/mL, and delivered through an IV administration set with a 0.2- or 0.22- μ m filter. Add 30.0 mL, ie, 1500 mg of durvalumab (MEDI4736) to the IV bag. The IV bag size should be selected such that the final concentration is within 1 to 20 mg/mL. The bag should be mixed by gently inverting to ensure homogeneity of the dose in the bag.

If participant weight falls to ≤ 30 kg, weight-based dosing at 20 mg/kg will be administered using an IV bag size selected such that the final concentration is within 1 to 20 mg/mL.

Standard infusion time is 1 hour \pm 10 minutes, however if there are interruptions, the total allowed time should not exceed 8 hours at room temperature.

Do not co-administer other drugs through the same infusion line.

[figure not shown]
The IV line will be flushed according to local practices to ensure the full dose was administered. Infusion time does not include the final flush time.

If either preparation time or infusion time exceeds the time limits, a new dose must be prepared from new vials. Durvalumab (MEDI4736) does not contain preservatives, and any unused portion must be discarded.

6.1.2 Dose and treatment regimens

Patients will receive 1500 mg durvalumab (MEDI4736) monotherapy via IV infusion q4w for up to a maximum of 24 months from Cycle 1 Day 1 (up to 26 doses/cycles) with the last administration at Week 104 (Figure 3). The study drug should be discontinued prior to 24 months if there is clinical progression or confirmed radiological progression or if there is unacceptable toxicity, withdrawal of consent, or another discontinuation criterion is met. Please note, if a patient's weight decreases to ≤ 30 kg, the patient should receive weight-based dosing equivalent to 20 mg/kg of durvalumab (MEDI4736) q4w after consultation between the Investigator and Study Physician, until the weight improves to >30 kg, at which point the patient should start receiving the fixed dosing of durvalumab (MEDI4736) 1500 mg q4w.

Figure 3 Durvalumab (MEDI4736) monotherapy dosing schedule

^a Or until discontinuation of study drug due to any of the reasons listed in Section 7.1.

Max.: Maximum; PD: Progression of disease; q4w: Every 4 weeks.

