1.2 Schedule of assessments

The procedures for the screening and treatment periods in this study are presented in [Table 1](#), and the procedures for the follow-up period are presented in [Table 2](#) (Schedule of assessments [SoA]).

Whenever vital sign assessments and blood draws are scheduled for the same nominal time, the assessments should occur in the following order: vital signs and then blood draws. Whenever electrocardiograms (ECGs), vital signs assessments, and blood draws are scheduled for the same nominal time, the assessments should occur in the following order: ECG, vital sign assessments, and then blood draws.

Patients may delay dosing due to immune-mediated adverse events (imAEs) or non-imAEs or for reasons other than TRAE.

- In case of imAEs or non-imAEs, dosing may be delayed per the Dosing Modification and Toxicity Management Guidelines (Section [8.4.5](#)).
- If dosing must be delayed for reasons other than TRAEs, dosing will resume as soon as feasible.

One cycle of treatment with the IP is equal to 28 calendar days.

Dosing intervals of subsequent cycles may be shortened as clinically feasible in order to gradually align treatment cycles with the schedule of tumour efficacy (RECIST) and PRO assessments. Subsequent time between 2 consecutive doses cannot be less than 22 days, based on the half-life of durvalumab (MEDI4736) (see current Investigator Brochure [IB]).

If imaging procedures were performed for alternate reasons prior to signing consent, these can be used for screening purposes with consent of the patient. However, all screening imaging results must have been obtained within 28 days of first IP dose administration.

PROs and tumour efficacy (RECIST) assessment dates are not affected by dose delays and remain as originally scheduled, as they are based on the date of first IP administration (not the date of therapy).

All other scheduled assessments must be performed relative to the start of the dosing cycle such that all laboratory procedures, etc, required for dosing should be performed within 3 calendar days prior to dosing.

| | Screening | C1 ^a | C2 ^a | C3 ^a | C4 ^a | C5 to PD (max. 24 months) ^{a,b} | | For details see Section | |
|------------------------------------|-----------|-----------------|--|-----------------|-----------------|--|-------------|-------------------------|-----|
| Week | -4 to -1 | 1 | q4w ±3 days unless dosing needs to be held for toxicity reasons | | | | Final visit | | |

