4.4 End of study definition

The end of the study is defined as the last visit of the last patient undergoing the study. A patient is considered to have completed the study when he/she has completed his/her last study visit per protocol.

The final DCO is planned to occur when the last patient had the opportunity to receive durvalumab (MEDI4736) for a maximum of 24 months, followed by a 90-day safety follow-up period post the last dose of IP.

At the final DCO, the clinical study database will close to new data. However, patients will be permitted to continue to receive IP beyond the closure of the database if a rollover or safety extension study is available at the time of the final DCO and, in the opinion of the Investigator, they are continuing to receive benefit from IP. For patients who do continue to receive IP beyond the time of the final DCO, Investigators will continue to report all SAEs to AstraZeneca Patient Safety until 90 days after last IP dose, in accordance with Section 8.4.1. If an Investigator learns of any SAEs, including death, at any time after a patient has completed the study, and he/she considers there is a reasonable possibility that the event is causally related to the study drug, the Investigator should notify AstraZeneca Patient Safety.

Any SAE or non-serious AE ongoing at the time of this final DCO is to be followed up at the discretion of the Investigator and per local practice and in alignment with the Dosing Modification and Toxicity Management Guidelines (Section 8.4.5), unless the event is considered by the Investigator to be unlikely to resolve or the patient is lost to follow-up.

See [Appendix A, A 6](#) for guidelines for the dissemination of study results.

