At the time of the final DCO, the analysis portion of the clinical study will have been completed and all patients remaining in the study will be considered to have completed the analysis portion of the study. At the time of final DCO, the clinical study database will be closed to new data.

Patients in OS follow-up (progressed and have discontinued treatment) will be considered to have completed the study.

Patients who are receiving treatment at the time of final DCO may continue receiving IP if the Investigator judges that they are gaining clinical benefit.

All patients will receive scans and follow-up care in accordance with standard local clinical practice. All data will be recorded on patient charts but will not otherwise be reported for the purposes of this study.

For patients who do continue to receive IP beyond the time of the final DCO, Investigators will report SAEs to AstraZeneca Patient Safety via paper case report forms (CRFs) until 90 days after the last dose of study drug, in accordance with Section 8.4.1. Any SAE or non-serious AE ongoing at the time of the DCO is to be followed up at the discretion of the Investigator and per local practice and in alignment with the Dosing Modification and Toxicity Management Guidelines (Section 8.4.5), unless the event is considered by the Investigator to be unlikely to resolve, or the patient is lost to follow-up. Data will not be captured for the purposes of this study outside of being recorded in the patients' source documents.

Following the DCO, SAE reporting applies only to patients who are active on IP and within 90 days after the last dose; in all other cases, only a Statement of Death notification is to be sent to AstraZeneca.

Different drug supply options will be available depending on the country, and these will be proposed to the patient when the most appropriate alternatives for continued treatment have been agreed between AZ and the investigator. Options may include the participation in a new rollover study or, if the study drug has been locally approved for use in this disease indication, patients may be discontinued and switched to the marketed product, in accordance with local laws.

In the event that a rollover or safety extension study is available at the end of 24 months of study treatment, or at the time of the final DCO / database closure, patients currently receiving

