6.6 Treatment after the end of the study

After the final analysis, AstraZeneca will continue to supply the IP to patients up to the time that they discontinue the treatment for whatever reason (see Section 6.1.3).

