##### **4.1.4.1 Visit Windows for Safety and PRO Assessments**

The following conventions will apply for safety and PRO data:

- The time windows should be exhaustive so that data recorded at any time point has the potential to be summarized. Inclusion within the time window should be based on the actual date and not the intended date of the visit.
- All unscheduled visit data will have the potential to be included in the summaries.
- The window for the visits following baseline will be constructed in such a way that the upper limit of the interval falls half way between the two visits (the lower limit of the first

post-baseline visit will be Day 2). If an even number of days exists between two consecutive visits, then the upper limit will be taken as the midpoint value minus 1 day.

For example, the visit windows for vital signs data are:

- Week 1; nominal day 1, visit window Day 1
- Week 4; nominal day 29, visit window 2 – 42
- Week 8; nominal day 57, visit window 43 – 70
- Week 12; nominal day 85, visit window 71 – 98
- Week 16; nominal day 113, visit window 99 – 126
- Visits after treatment discontinuation will be assigned to the last treatment cycle for up to 15 days only. Visits after the 15 days will contribute to the following 30 days post treatment discontinuation interval, see below.
- Visits up to 90 days after last dose will be assigned similarly to the definition for the visits under treatment, but for 30 day intervals after treatment discontinuation, eg,:
  - 30 days after last dose, visit window 16 – 45
  - 60 days after last dose, visit window 46 – 75
  - 90 days after last dose, visit window 76 – 97
  - Data recorded after 97 days after last dose will not contribute to the analysis period of up to 90 days following the date of last dose, and will not be re-mapped
- For summaries showing the maximum or minimum values, the maximum/minimum value recorded on treatment will be used (regardless of where it falls in an interval).
- Listings should display all values contributing to a time point for a patient.

For visit based summaries:

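### Protocol 6.1.2 sets the maximum at 26 doses and also at a last infusion in Week 104, and on an undelayed 28-day schedule the two do not agree

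*Protocol*

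**What the plan says.** Protocol 6.1.2 expresses one maximum in three ways: 24 months from Cycle 1 Day 1, a dose count, and a week. The last two are given together as "up to 26 doses/cycles) with the last administration at Week 104", with a reference to Figure 3, which is not reproduced in the public text. The dosing interval is fixed elsewhere. Protocol 1.2 states that "One cycle of treatment with the IP is equal to 28 calendar days", and the note to Table 5 in 6.1.1 states that "Cycles of durvalumab (MEDI4736) administration are 28 days".

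Two ways of numbering weeks are in use. The SAP's visit windows (4.1.4.1) run on elapsed weeks after the first visit: "Week 4; nominal day 29, visit window 2 – 42". Protocol Table 1 labels Day 1 as Week 1.

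On treatment at the end of the study, Protocol 4.4 says "The final DCO is planned to occur when the last patient had the opportunity to receive durvalumab (MEDI4736) for a maximum of 24 months". It adds 90 days of safety follow-up to that, and SAP 5 times the final analysis the same way. Section 4.4 then permits drug after database closure on two conditions: a rollover or safety extension study is available, and the investigator sees continuing benefit. Section 6.1.3 says "Patients who are receiving treatment at the time of final DCO may continue receiving IP if the Investigator judges that they are gaining clinical benefit". Section 6.6 says "AstraZeneca will continue to supply the IP to patients up to the time that they discontinue the treatment for whatever reason", with a cross-reference to 6.1.3.

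**The concern.** A dose count and a last-dose week are two descriptions of the same limit, so a site should reach the same stopping point from either. Here they are one 28-day cycle apart. A patient who has had 26 infusions on schedule reaches Day 729 with one figure saying the limit has been met and the other naming that week for an infusion.

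At stake are one 1500 mg infusion per completer, the date of the last dose, and a final cut-off that 4.4 ties to the last dose plus 90 days.

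The secondary matter is the text on treatment after the final cut-off. It provides for patients still on drug at a time when, under the 24-month limit, none should be, and the sections do not set the same condition for continuing.

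**Working it through.** **Inputs.** 26 doses and Week 104 (Protocol 6.1.2); 28-day cycles (Protocol 1.2 and Table 5 note); first dose on Day 1 and a 24-month maximum (Protocol 4.1 and 6.1.2); Week 4 = Day 29 (SAP 4.1.4.1); Day 1 in Week 1 (Protocol Table 1); 90 days before the final cut-off (Protocol 4.4).

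**1. The plan's own pair of figures.** 26 cycles × 28 days = 728 days = 104 weeks. So 26 and 104 do belong together, but as a number of cycles and the time at which the last of them ends. A dose opens its cycle, so this does not place an infusion at Week 104.

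**2. Day of each dose.** Dose k falls on Day 28(k − 1) + 1. As a check, dose 9 gives 28 × 8 + 1 = 225, the day shown for the ninth dose in SAP Table 5.

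| Dose | Day | Week, SAP numbering | Week, if Day 1 is in Week 1 |
|---|---|---|---|
| 26 | 28 × 25 + 1 = 701 | 700/7 = 100 | 101 |
| 27 | 28 × 26 + 1 = 729 | 728/7 = 104 | 105 |

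Neither numbering puts an undelayed dose 26 in Week 104. In the second numbering Week 104 is Days 722 to 728, which holds no nominal dose. The nearest is dose 27, which a three-day-early visit would bring to Day 726.

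**3. Delay needed to make both figures true.** 729 − 701 = 28 days, or a mean interval of 728/25 = 29.12 days over the 25 intervals.

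**4. Does the 24-month limit decide it?** 24 × 365.25/12 = 730.5 days (the SAP uses Day 730 for 24-month estimates). Day 729 is inside. Since 730.5/28 = 26.09, there is room for 26 full intervals and therefore 27 infusions. The limit does not choose between the two figures.

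**5. Size per completer.** 26 × 1.5 g = 39.0 g against 27 × 1.5 g = 40.5 g, a difference of 1.5 g (1.5/39.0 = 3.8%). The last dose is Day 701 or Day 729, and 90 days later is Day 791 or Day 819.

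**6. Exposure measures.**
- Relative dose intensity (SAP 3.2.8) counts intended dose only to discontinuation, progression or cut-off, whichever comes first. Patient 2 in SAP Table 5 stops after 8 doses, has an intended dose of 12 g and scores 100%. By the same rule a patient who stops after 26 on-schedule doses has 39.0/39.0 = 100%, whichever figure in 6.1.2 is right.
- Percentage intended dose runs to progression, a censoring event or cut-off. If the intended dose were capped at the 6.1.2 maximum, 26 doses would score 26/26 = 100% or 26/27 = 96.3%. The SAP states no such cap, and SAP 4.5.5 does not list this measure among the exposure summaries.

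**7. Final cut-off.** For the last patient it is Day 791 or Day 819 if counted from the last dose, or 730.5 + 90 = 820.5 if counted from 24 months. That is 60.5 to 90 days past the 24-month limit, and longer for every patient who started earlier.

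**The case against.** The best defence of 6.1.2 is that Week 104 is loose wording for the end of cycle 26. Numbered from Week 1, 26 cycles fill Weeks 1 to 104 exactly. Delays are also allowed, and delays adding up to 28 days would put dose 26 at Week 104. Figure 3 may make the intention clear. All of this is plausible, and it is why Week 104 cannot simply be called the 27th dose: that holds in the SAP's numbering only. But the sentence speaks of an administration, describes the planned schedule and mentions no delay, so the defence explains the slip without removing it.

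A reader might infer more than the documents support:

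- **That a 27th dose complies with one clause.** The same sentence sets an upper limit of 26, and both limits apply together, so a 27th infusion would break an explicit number. That sites will in fact differ is conjecture.
- **That intended dose changes for every completer.** Relative dose intensity does not change, and the 96.3% needs a cap that the SAP does not state.
- **That safety follow-up is lost.** It is timed from each patient's actual last dose (Protocol 7.1.1 and Table 2), so it moves with that dose.
- **That exposure and non-serious adverse events after the final cut-off go missing.** Under the 24-month limit no compliant patient is on drug at the planned cut-off, so there is nobody to lose. The text could still serve if the cut-off came early.
- **That 6.6 gives open-ended supply.** It refers back to 6.1.3, which repeats the 24-month maximum and names a rollover study or marketed product as possible routes.
- **That the Figure 2 note adds a further rule.** It speaks of the cut-off without saying final, and patients could properly still be on drug at the six-month primary analysis.

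What stands against 6.1.3 is narrower. Its permission rests on the investigator's judgement alone, and it says only that options may include a rollover study or marketed product. Section 4.4 makes availability of a rollover or extension study a condition.

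**Conclusion.** The main point holds. Protocol 6.1.2 gives a dose count and a last-dose week that differ by one cycle on an undelayed schedule, and the 24-month limit does not resolve it. The ambiguity is one 1500 mg infusion and 28 days of last-dose timing per completer, and up to 28 days in a final cut-off counted from the last dose. The primary endpoint stops at Day 183 (SAP 3.2.1) and is not affected, nor is relative dose intensity. Percentage intended dose would be affected only if its intended dose is capped at this maximum.

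The secondary point also holds, as a failure to harmonise: 4.4 and 6.1.3 set different conditions for drug after a final cut-off that already lies beyond the cap.

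This rests on exact 28-day intervals from Day 1, on Week 104 naming an infusion as the text says, and on Figure 3, which was not available, not correcting the sentence. It is an error in an operative figure, worth correcting, with no bearing on the main safety result.

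**What to change.** Reconcile the passages. Section 6.1.2 and Figure 3 should give a dose count and a week of last permitted administration that agree, and should say how weeks are numbered. If percentage intended dose is to be reported, SAP 3.2.8 should say whether intended dose is capped at that maximum. Sections 4.4, 6.1.3 and 6.6 should state one rule on whether, and under what arrangement, drug may be given after the final cut-off. Which limit and which rule apply is for the sponsor to decide.

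The cost is a few lines of protocol wording, a check of Figure 3 and at most one line in the SAP. No analysis or sample-size figure has to be redone.
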